Statistical Analysis Plan

"MyoVoice to Restore Natural, Hands-free Communication to Individuals With Vocal Impairments"

NCT04762043

IRB Approved 6-26-2023

The goal of our statistical design is to achieve secondary endpoints that are analyzed post hoc. This is not the type of clinical trial in which endpoints result from subjects being randomized and for which the trial is powered. Instead, our statistical plan was designed to assess the perceived naturalness ratings of our Phase II sEMG-based silent-speech synthesizer by comparison of ratings with 3 alternative synthesized speech modalities that including: electrolaryngeal speech (EL), synthesized speech with a flat prosodic contour (SP), and synthesized speech with a prosodic contour generated by our Phase I algorithms (GP). Each sample was rated on a visual analog scale from 0 to 100, which 0 anchored at "least natural" and 100 anchored at "most natural." A mixed effects model will be used to demonstrate that the effects of both listener (i.e. random effect) and speech type (fixed effect) meet a level of significance (p<0.05) have a significant effect on the speech naturalness ratings. Post-hoc testing using a Tukey analysis will be used to make pair-wise comparisons across the SP, GP, and FP methods.

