# **Involvement of Human Subjects**

*Human Subjects Involvement and Characteristics:* [name], a Research Scientist at Altec, Inc., will coordinate the involvement of human subjects in the proposed project. She will work closely with the PI, [name] [name], and Secondary Study Coordinator, [name], to ensure that all aspects of human subject screening, enrollment, and testing complies with Federal regulations involving voluntary participation of human subjects in research, as determined by WCG IRB.

Human subject involvement will consist of the voluntary participation of adults for data collection experiments described in the Research Strategy. These experiments are of two types:

• Study 1(a): Collection of sensor and/or voice data during experiments in which subjects either read out loud and/or subvocally recite vowels by themselves, read text provided on a computer screen, and answer questions to elicit spontaneous speech; and

Study 1(b): Listener experiments in which naïve control subjects listen to speech samples and
make judgments about certain characteristics of the speech, such as how well they can correctly
identify the vocabulary words (i.e., compute their word error rate) or distinguish between
different speakers (i.e., evaluate personalization of digitized speech). The involvement of human
subjects is described in greater detail for each experiment category:

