# Study 1(b): Listening experiments to evaluate recognition of synthesized voices

This portion of the study will be limited to n=10 subjects with healthy voices. Subjects must speak and be literate in English so that they can understand instructions, as well comprehend speech recordings that will be presented to them in English. We will seek recruits with no clinical experience with laryngectomees. Listeners must also be comfortable in typing phrases into a computer using a keyboard and mouse. Both males and females will be included in equal numbers so that possible sex-specific differences can be accommodated for men and women during the experiments. We will exclude candidates with conditions which might disqualify them for participation – such as poor hearing, speech disorders, or memory disorders that are identified through an initial interview screening.

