Description of Test Procedures: The experiments will take place in the research facilities of Altec Inc. under the supervision of the PI and the assistance of [name] and [name]. Listening experiments will require 1–2 hours. Study participants will first undergo a brief hearing screening at 1000, 2000, and 4000 Hz randomly to each ear at 25dB through the headphones of an audiometer (Maico Diagnostics MA-27). Any participant who is unable to hear any of the three tones in both ears will have failed the screening test and will be compensated for their time/transportation and dismissed. After the hearing screening, subjects will be seated at a computer workstation in a quiet office setting. They will be instructed to listen to a series of short phrases through speakers or headphones that are like the phrases in Experiment 1(a). Subjects will be prompted at the completion of each phrase to make judgments about certain characteristics of the speech, including the acceptability of the speaker's voice, the identity of the speaker, and the emotion conveyed within the message. The criteria on which to judge acceptability will be based on acceptability instructions advocated by Bennett and Weinberg which includes the speaker's fluency, rate, inflection, and "pleasant" quality. Subjects will also be instructed to orthographically transcribe the phrase they heard (i.e., to assess intelligibility) and answer a question about the phrase (i.e., to assess comprehensibility). Answers will be entered by the subject using a keyboard and mouse in a field visible on the screen below the prompt. The subject will be able to control when a new prompt appears and can interrupt the testing at any time to rest or ask a question. There will be no sensor recordings in this experiment or any instrumentation other than the computer and acoustic stimuli. Recruitment: Same as described for control subjects in Experiment 1(a)

**Potential Risks/Minimizing Risks:** The primary risk/discomfort will be boredom or fatigue associated with the relatively long duration of the experiment. We will provide the same mitigating activities (rest, refreshments, etc.) as in Experiment 1(a) description. No risks associated with the use of sensors are a factor in this portion of the study.

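### The SAP names electrolaryngeal speech (EL) as a comparator for the Phase II synthesizer, but its Tukey step covers only SP, GP and an undefined FP, so no pairwise test against EL is planned

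*SAP*

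**What the plan says.** The SAP is a single paragraph about one outcome, naturalness rated from 0 to 100. Its stated purpose is that "our statistical plan was designed to assess the perceived naturalness ratings of our Phase II sEMG-based silent-speech synthesizer", and it does this "by comparison of ratings with 3 alternative synthesized speech modalities that including: electrolaryngeal speech (EL"), together with SP (flat prosodic contour) and GP (contour from the Phase I algorithms). That makes four speech types: the Phase II system and three alternatives.

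The model has listener as a random effect and speech type as a fixed effect, at p<0.05. The last sentence then limits the Tukey pairwise comparisons to SP, GP and FP. EL is not in that list, and FP appears nowhere else in either document.

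The SAP also says that its endpoints are secondary and analyzed post hoc, and that the trial is not powered for them.

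Four places in the protocol bear on this:
- Specific Aims of Study, Aim 3, calls the electrolarynx the gold standard. The evaluators there are people with total laryngectomy and their speaking partners.
- Study 1(b) uses different listeners: "This portion of the study will be limited to n=10 subjects with healthy voices". Involvement of Human Subjects describes them as naive.
- The Study 1(b) test procedures have listeners judge acceptability, "the identity of the speaker, and the emotion conveyed within the message". They also state: "Subjects will also be instructed to orthographically transcribe the phrase they heard (i.e., to assess intelligibility"), and listeners "answer a question about the phrase (i.e., to assess comprehensibility"). Naturalness is not named.
- Involvement of Human Subjects names a metric for the transcription task: how well listeners "identify the vocabulary words (i.e., compute their word error rate").

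**The concern.** The comparison with EL asks whether the new system sounds more natural than an aid that people with laryngectomy already use. The SAP lists EL first among its comparators and then leaves it out of the only step that compares speech types two at a time. Followed as written, the plan can show how the synthesized methods rank against one another and still give no estimate or test of Phase II against EL.

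The undefined FP adds to this. A reader cannot confirm from the documents that the Phase II system is in the pairwise step.

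If an EL comparison is reported later, its method and multiplicity adjustment will not have been written down. The three planned pairs and the EL pairs could then be judged by different standards.

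**Working it through.** The documents give no power, SD or effect size, so there is no sponsor figure to reproduce. The check is a count of pairs, a look at what the overall test can show, and the price of adding EL.

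**Pairs**
- Speech types named in the SAP: the Phase II system, EL, SP, GP, so k = 4. Possible pairs: k(k−1)/2 = 4×3/2 = 6.
- Methods in the Tukey sentence: SP, GP, FP, so k = 3. Planned pairs: 3×2/2 = 3 (SP–GP, SP–FP, GP–FP).
- If FP is the Phase II system, 6 − 3 = 3 pairs are left out: EL–SP, EL–GP and EL–FP. All three involve EL.
- If FP is not the Phase II system, none of the planned pairs contains it.

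**Whether the overall test fills the gap**

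The test of speech type has the null hypothesis that all type means are equal. Rejecting it says only that at least one difference exists. For example, SP could differ from the other three types while Phase II and EL have the same mean, and the overall test could be significant. The three planned pairs cannot supply the contrast either, because none of them contains EL.

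**Price of including EL**

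Assumptions: the 10 Study 1(b) listeners are the raters, each contributes one mean rating per speech type, and EL is already a level in the model. Error df = (10−1)×(4−1) = 27 for either family of comparisons. The Tukey multiplier on the t scale is q/√2 at the 0.05 level.

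| Family | q | q/√2 |
|---|---|---|
| 3 methods, df 27 | 3.506 | 2.479 |
| 4 methods, df 27 | 3.870 | 2.737 |

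- Ratio: 2.737/2.479 = 1.104, so each interval is about 10% wider.
- Large df: 2.34 to 2.57, ratio 2.57/2.34 = 1.10, so also about 10%.
- If EL pairs were added but all six were judged at the 3-method value of 2.479, the familywise error would be about 8.6%, not 5%. Naming the four-method family in advance avoids this.

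**The case against.** The best defense is that the SAP is openly exploratory. It declares its endpoints post hoc and the study unpowered, and it makes no confirmatory claim against EL. EL is a listed modality and, on a natural reading, a level of the fixed effect, so it is not absent from the analysis. These points stand, and they limit how serious the omission is. They do not remove it, because the SAP itself names EL as a comparator and an exploratory plan can still report the contrast.

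A reader might infer more than the documents support:
- *That EL is dropped from the analysis.* Only the pairwise step leaves it out.
- *That the plan omits its own gold standard for naturalness.* The gold-standard wording belongs to Aim 3, and the SAP does not say that its listeners are the Aim 3 participants. The firmer basis is the SAP's own comparator list.
- *That five pre-declared endpoints lack an analysis.* The SAP does give none for acceptability, speaker identity, emotion, transcription or comprehension. But the protocol presents these as listener tasks in a human-subjects description and does not label them endpoints. It also refers to a Research Strategy that is not among these documents. In a study that calls its analyses post hoc, this is mostly missing detail.
- *That naturalness was not collected.* The Study 1(b) list of judgments is open-ended, so naturalness is unnamed there, not excluded.
- *That the precision of an intelligibility comparison can be judged.* The documents give no SDs, accuracy rates or item counts. They say only that listeners will "listen to a series of short phrases through speakers or headphones that are like the phrases in Experiment 1(a"), without stating which speech types they hear.

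**Conclusion.** The point holds for the pairwise step. No pairwise test of Phase II against EL is planned for naturalness, although the SAP names EL as a comparator, and the overall speech-type effect cannot stand in for it. Under the reading that FP is the Phase II system, 3 of 6 pairs are planned and 0 of the 3 EL pairs. That reading is plausible but not documented; if it is wrong, the gap is larger.

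The counts rest on the SAP text alone apart from the reading of FP. The 10% cost at df 27 rests on the assumptions stated with the calculation, and it is about the same for large df.

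Two secondary matters need reconciling, not redesign. One is whether the SAP's listener is the Study 1(b) naive listener or the Aim 3 participant. The other is where naturalness was rated. The lack of an analysis for transcription and comprehension is true of the SAP, but it supports no more than a request for descriptive reporting.

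**What to change.** Define FP, and replace the last sentence of the SAP with wording such as: *Tukey-adjusted pairwise comparisons of naturalness will be made across all four speech types (EL, SP, GP and the Phase II method). The Phase II minus EL difference will be reported with its adjusted 95% confidence interval.*

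Add a short reconciling statement that says who the listeners were (Study 1(b) naive listeners or Aim 3 participants) and where the naturalness ratings were collected.

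For the transcription and comprehension tasks, word error rate and the percentage of questions answered correctly could be reported descriptively for each speech type presented. They should be labelled post hoc, as the SAP already labels its endpoints. The documents do not support prescribing a model for them.

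The cost is a few lines of SAP wording and naturalness intervals about 10% wider. If EL samples were rated together with the other types, as the SAP's comparator list implies, no new data are needed. If they were not, the SAP should say that this contrast cannot be estimated.

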#### **Specific Aims of Study**

In Aim 1, we translate our Phase I proof-of-concept phrase-level prosody recognition algorithms to ones that can transcribe within-phrase prosodic speech and track variations in prosody (pitch, loudness, and duration) to create linguistic boundaries, clarify lexical ambiguities, and convey emotional intent. To carry out this work, we acquired simultaneous acoustic and sEMG recordings as individuals with healthy voices speak a corpus of phrases comprising an extensive set of prosodic-phonemic combinations to elucidate the relationship between acoustic and sEMG representations of prosody. The data set was used to design new multi-level dynamic learning algorithms to identify person-specific variations in prosody based on a set of selected sEMG features. We also redesigned our Phase I subvocal speech algorithms that leverage the sEMG data to transcribe lexical content amidst the multitude of variations in pitch, loudness, and duration that exist in prosodic speech.

In Aim 2, we advanced our Phase I sensor and algorithm development efforts for conversational use by developing software to manage interactions between the sEMG sensors and our speech algorithms developed in Phase I. The Aim 1 algorithms were trained on a reduced sensor subset, and subsequently achieved comparable algorithmic performance with a smaller number of sensors that will be incorporated into a newly designed custom-fit, reusable sensor veneer to facilitate non-expert sensor placement for repeatable algorithmic performance for the individuals with total laryngectomy.

In Aim 3, the prototype MyoVoice™ system developed in Aims 1 and 2 was evaluated for social reception amongst persons with total laryngectomy and their primary speaking partner. Each participant evaluated the speech outputs from our sEMG-to-speech against the current gold-standard, electrolarynx. When evaluated for conversational efficacy, our MyoVoice™ system will be shown to yield greater preferences toward synthetic speech that integrates linguistic prosody based on fine-tuned estimates of pitch and loudness. The resulting pre-commercial AAC system will have broad-reaching impact for introducing a level of social interaction from an AAC device that is unprecedented among individuals living with articulatory-based vocal impairments.

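### The SAP lists electrolaryngeal speech as a comparator for the Phase II synthesizer, but its only pairwise step leaves that comparison out

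*SAP*

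**What the plan says.** The SAP is a single paragraph. It opens with "The goal of our statistical design is to achieve secondary endpoints that are analyzed post hoc" and adds that the study is neither randomized nor powered. Its purpose is to assess the naturalness of the Phase II synthesizer by "comparison of ratings with 3 alternative synthesized speech modalities that including: electrolaryngeal speech (EL"), followed by synthesis with a flat contour (SP) and synthesis with a contour from the Phase I algorithms (GP). The Phase II output is given no abbreviation.

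Ratings are on a 0–100 visual analog scale. A mixed effects model takes listener as random and speech type as fixed, judged at p<0.05. The only pairwise step is "Post-hoc testing using a Tukey analysis will be used to make pair-wise comparisons across the SP, GP, and FP methods".

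The protocol bears on EL in Aim 3 (Specific Aims of Study): "Each participant evaluated the speech outputs from our sEMG-to-speech against the current gold-standard, electrolarynx".

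**The concern.** The list of comparators and the list of pairwise tests do not match. EL is in the first and absent from the second. FP is in the second and defined nowhere in the SAP or protocol.

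Followed as written, the SAP gives no test and no interval for Phase II against EL on naturalness, the only outcome it analyses. A significant speech-type effect could come from any pair and carries no direction. An EL contrast added later would be unplanned, although the SAP presents EL as a comparator from the start and Aim 3 calls the electrolarynx the gold standard.

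**Working it through.** **1. Match the two lists.** Both come from the SAP.

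| Speech type | Named in the aim | Named in the Tukey step |
|---|---|---|
| Phase II output | yes (no abbreviation) | only if FP means this |
| EL | yes | no, unless FP is a slip for EL |
| SP (flat contour) | yes | yes |
| GP (Phase I contour) | yes | yes |
| FP | not named | yes, undefined |

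**2. Work through the meanings of FP**, taking SP and GP as the SAP defines them. The Tukey set has three members and two are fixed, so one place is left.

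- FP is the Phase II output: Phase II versus SP and versus GP are tested; Phase II versus EL is not. One of 3 intended comparisons is missing.
- FP is EL, a second label for flat prosody, or anything else: the Phase II output is in no pair. All 3 are missing.

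Phase II versus EL is absent in every case.

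**3. Count the pairs.** With k types there are k(k−1)/2 pairs.

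- Planned set, k = 3: 3×2/2 = 3
- Four types named in the aim, k = 4: 4×3/2 = 6
- If FP is a further type, k = 5: 5×4/2 = 10

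Steps 1 to 3 need no assumption about raters or variability.

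**4. Illustrate the cost of the larger family.** The documents state no power or sample size for the ratings, so there is no figure to reproduce. The raters are not identified either. Study 1(b) is "This portion of the study will be limited to n=10 subjects with healthy voices", but the judgments it lists (acceptability, "the identity of the speaker, and the emotion conveyed within the message", transcription and a comprehension question) do not include naturalness. Aim 3 describes a system "evaluated for social reception amongst persons with total laryngectomy and their primary speaking partner". I therefore assume 5, 10 or 20 raters.

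Other assumptions: one mean rating per rater and type; the difference d is in units of the residual SD of that mean.

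- Error df = (types in model − 1)(n − 1)
- Critical |t| = q(0.95; types compared, df)/√2, with q the studentized range quantile
- Power for one pair: noncentral t with noncentrality d√(n/2). For n = 10, d = 1.5: 1.5×√5 = 3.35

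| n | Types compared | EL in model | df | Critical \|t\| | Power at d = 1.5 |
|---|---|---|---|---|---|
| 10 | 3 | no | 18 | 2.552 | 0.780 |
| 10 | 3 | yes | 27 | 2.479 | 0.803 |
| 10 | 4 | yes | 27 | 2.737 | 0.727 |
| 10 | 5 | yes | 36 | 2.871 | 0.683 |
| 5 | 3 | no | 8 | 2.857 | 0.375 |
| 5 | 3 | yes | 12 | 2.668 | 0.417 |
| 5 | 4 | yes | 12 | 2.969 | 0.324 |
| 20 | 3 | no | 38 | 2.439 | 0.987 |
| 20 | 3 | yes | 57 | 2.406 | 0.989 |
| 20 | 4 | yes | 57 | 2.646 | 0.980 |

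With 10 raters, going from three to four types raises the critical value by 7% (2.737/2.552 = 1.072) or 10% (2.737/2.479 = 1.104).

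**The case against.** **EL can be in the mixed model.** It can, and the overall speech-type test may then use its data. The exact statement is that no pairwise test is planned. The overall test still does not answer whether the Phase II output differs from EL.

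**FP is plainly the Phase II output.** That is the most plausible reading, but an inference, and it still leaves EL out. Conversely, an undefined label might mean that SP or GP is also used loosely. The count of all 3 missing therefore holds only if SP and GP keep their stated meanings.

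**Aim 3 is not about naturalness.** It speaks of social reception and preference, and the SAP does not say its ratings are the Aim 3 evaluation. This stands: Aim 3 is context only. The SAP's own comparator list is enough to support the point.

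**Six pairs are more than the aim needs.** The aim is Phase II against three alternatives. A many-to-one (Dunnett) procedure with 10 raters and 27 df has a critical |t| of about 2.49 and power of about 0.80 at 1.5 SD, against 2.74 and 0.73 for four-type Tukey. That is a legitimate alternative, at the price of dropping SP versus GP from the family. It does not make four-type Tukey unsound, and four-type Tukey completes the method the SAP already chose.

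**Everything here is post hoc.** True, and it limits the harm. A descriptive plan should still contain the comparisons it says it was designed to make.

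**Conclusion.** The concern holds. Phase II versus EL is a stated comparison with no planned pairwise test. The minimum gap is 1 of 3 intended comparisons (FP is the Phase II output) and the maximum is all 3 (FP is anything else); 3 of the 6 possible pairs among the four named types are planned at most. This rests on the SAP's own definitions of SP and GP and on no numerical assumption. Only the power figures depend on assumed rater numbers and data structure. The point should be fixed, but because the SAP claims neither power nor confirmatory status, it does not undermine a confirmatory result.

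**What to change.** Define FP or correct the label. Then replace the Tukey sentence with:

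> Tukey-adjusted pairwise comparisons will be made across all four speech types (EL, SP, GP and the Phase II output; 6 pairs), each reported with its adjusted 95% CI and p-value.

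- If FP proves to be a further type, keep it in the family (5 types, 10 pairs).
- If only the comparisons with the Phase II output matter, a prespecified Dunnett set of 3 contrasts is acceptable, stating that SP versus GP is then outside the family.
- If EL was left out of the pairwise tests on purpose, give the reason and amend the comparator list so that the aim and the tests agree.
- The SAP describes the rating in the past tense. If ratings have already been analysed, label the EL contrasts as added afterwards.

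The cost is one or two sentences and no new data. Some power is lost for the pairs already listed: small with 10 or 20 assumed raters, more noticeable with 5, where power was low in any case.
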